We aim to protect participant data and personal information by using de-identified participant ID numbers in place of participants' names. Participant data will be de-identified. This is to maintain participant confidentiality when entering survey responses and Fitbit data. Data that is collected will be accessible only to the research study staff. All data will be kept in secure databases that are password protected and to which only study personnel have access. The databases that will be used during the study are: REDCap and CareEvolution. CareEvolution will have access to the information that is input into the apps, including the answers to the survey and Fitbit data. Fitbit will also have access to the Fitbit data (i.e. step count, heart rate, sleep and calorie data). Again, to protect participants information, we will assign participants a study ID so that data will be de-identified when data transfers occur. The secure database REDCap will be the only place that will have the linkage between the participants de-identifier and name. All data collected from participants will be destroyed 10 years after the final completion of the study. It is also important to note that data uploaded in CareEvolution will be securely stored on servers in the United States or by third party service providers that CareEvolution works with to store and secure information in the United States.

27. Provisions to Protect the Privacy Interests of Subjects

All participants will be told that their participation is voluntary and that they are free to not respond or to terminate involvement at any time with no adverse consequences.

Study subject ID numbers will be used and only the researchers will know the names of the subjects. We will assign each participant a study ID so that data may be de-identified for exports. If a participant does not want to use their email address when signing up for the Fitbit and MyDataHelps app, a research assistant will assign the participant a de-identified study email instead. All information obtained during the study will be considered confidential and will remain on secure servers and locked file cabinets.

To make participants feel at ease, all interviews will be conducted in private phone calls and/or video conference calls (Zoom), which will be password protected. The interviewer for the

INVESTIGATOR STUDY PLAN

phone/web-based video calls will be conducted in an enclosed private room with no other individuals present. We will only collect information needed to conduct the research. Participants will be told that they can skip any questions they want throughout the interview.

The contact information of the Principal Investigator will be given to all participants who participate in this study. Participants will also be asked if they are feeling uncomfortable during data acquisition, and if at any time the participant feels uncomfortable, he or she can choose to stop.

Protection for Risks Associated with Participating in Research Interviews

The study staff will inform all participants that their participation is voluntary, that they are free to not respond, or to terminate involvement at any time with no adverse consequences.

28. Compensation for Research-Related Injury

None; there are no resources available. We do not anticipate any research-related injuries. We believe the research poses no more than minimal risk to subjects.

29. Economic Burden to Subjects

The study apps can be used free of charge when a participant's phone is connected to Wi-Fi. Participants are responsible for any costs from their service provider related to talk/text/data usage if they choose to use the study application while disconnected from Wi-Fi.

30. Consent Process

All research personnel will read and be familiar with HRP-802: INVESTIGATOR GUIDANCE: Informed Consent. A consent form will be sent via a secure REDCap link to eligible individuals. Participants will also have the opportunity to ask any questions they may have before signing the consent form if they wish to participate. If they are interested in participating, they will provide their electronic signature. The study staff will retain their signed form and will store it on the secure REDCap database. For potential participants who do not have internet access and are unable to complete the online consent, we will ask if they would like a paper consent form mailed to their home address. Once they receive the consent form, we will ask them to call us back or we will call them back one to two weeks after mailing the form to review the consent with a study staff member. All questions will be answered, and the staff member will ask if they agree to participate in the study. If yes, this verbal consent will be documented by research staff in REDCap. Printed versions of the signed consent forms will be stored in a locked cabinet or locked file room that will only be accessible to research staff. Once the consent form is signed, we will assign a unique study ID to the participant. For Aim 3, we request to use Fact Sheet to obtain verbal consent to conduct interviews with providers and clinic staff (See Survivor mHealth A3 Fact Sheet.docx).

Waiver or Alteration of the Consent Process: We are requesting a waiver of written consent due to the minimal risk of the study. This study involves no procedures that require written consent outside of the research context.

INVESTIGATOR STUDY PLAN

31. Process to Document Consent in Writing

All research personnel will read and be familiar with HRP-803: Documentation of Informed Consent. The signed consent forms will be printed and kept in a locked cabinet or locked file room that will only be accessible to research staff. Signed consent forms will be retained for a minimum of 5 years after completion of the study.

We are seeking a waiver of written documentation of consent only for the subjects cited in #30 who do not return a signed paper consent, but who do undergo a verbal consent process that is documented by the research staff in REDCap.

32. Drugs or Devices

The study will deploy a Fitbit device to all participants to track progress of their physical activity. The Fitbit will collect data on participants' daily steps, heart rate, and sleep patterns. Please note that this software does not qualify as a medical device according to FDA guidance "Policy for Device Software Functions and Mobile Medical Applications", as it falls into the category listed in Appendix A, #17.

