*Medical clearance will be sought with patient's provider if needed (see smhealth_med_clearance)

Exclusion Criteria:

1. Is a prisoner
2. Non-English speaking
3. Is unable to provide consent
4. Under 18 years of age
5. No prior cancer diagnosis
6. Does not own a smartphone

Aim 3

Inclusion Criteria:

1. Are a current UMMHC Cancer Clinic patient navigator, oncologist, radiologist, or cardiologist
2. Consent to participate

Exclusion Criteria:

1. Not currently employed at UMMHC
2. Not involved in direct treatment of care coordination of cancer patients

Vulnerable Populations

Children

Children will not be included in the study population.

Prisoners

Prisoners will not be included in the study population.

Adults Unable to Consent

Adults unable to consent will not be included in the study population.

Pregnant Women

Pregnant women will be included in the study population.

7. Study-Wide Number of Subjects*

We will include up to 50 participants made up of cancer survivors, providers, and clinic staff.

8. Study-Wide Recruitment Methods*

N/A. This is not a multi-site study.

INVESTIGATOR STUDY PLAN

9. Study Timelines*

The overall project timeline is described in the table below (Table 1):

Table 1. Project Timeline

	Apr	May	June	July	Aug	Sep
IRB, recruitment of participants	X	X				
Wearing of the devices and completion of surveys to track data, transmission of the device data to the servers		X	X	X	X	
Data Analysis and data transfer				X	X	
Qualitative Interviews				X	X	
Study conclusion and write-up						X

The study is planned to take place over the course of six months but will be extended if need be until all goals are achieved. Primary analysis is expected to be complete by the end of six months.

Duration of an Individual Subject's Participation

Individual subjects in the Aim 1 pilot are expected to participate for no more than 90 days in the study. Aims 2 and 3 consist of one-time interviews.

10. Study Endpoints*

Primary Outcome Measure: To assess the feasibility of a wearable device and smartphone app digital health program in cancer survivors.

Secondary Outcome Measure: To assess usability, physical activity, and quality of life health outcomes measures. We will also qualitatively assess 1) participant experiences and improvements to be made to the program, and 2) provider and clinic staff perceptions of implementing referrals to digital health programs and accessing patient-generated health data. medical providers/clinic staff .

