The participant's Fitbit will receive automated Fitbit push notifications (See Survivor mHealth Pilot Push Notifications.xlsx) to promote adherence (e.g., "Keep it up"). The participant's smartphone will also receive push notifications from MyDataHelps to promote adherence to the study surveys and Fitbit. If participants are experiencing technical challenges or difficulties adhering to study protocols (e.g., syncing Fitbit, completing surveys), we may then contact participants by phone to troubleshoot potential issues. Overall, our main goal of the pilot study is to determine feasibility in this population using these devices, while obtaining feedback we can use to refine the study before launching a larger trial in cancer survivors.

Furthermore, study participants will download two apps onto their phone: Fitbit and MyDataHelps. The apps can be downloaded through the Apple App Store or Google Play Store. Instructions will be provided to participants on how to download and navigate these apps. The instructions will also include a unique study ID number for each participant. When a participant is signing up for the apps, they will use their assigned study ID as their first name. To further maintain confidentiality, all participants will be assigned the same last name "MHEALTH" when signing up for these apps.

INVESTIGATOR STUDY PLAN

The study ID will be used for data exports so that participants' names are de-identified. Participants may also choose if they would like to use their personal email address or a study generated email address to register for the MyDataHelps and Fitbit app. Through the MyDataHelps app, participants will complete a set of surveys at 24 hours after their enrollment, 1 month, and 3 months after enrollment (Table 2). The following surveys will be deployed to study participants: Quality of Life Health Status (FACT-G), MARS (app usability), and Physical Activity. Overall, the main purpose of these surveys is to make sure we can successfully obtain data and to receive feedback on the usability of the devices and app. Subjects will not be explicitly told that they should explore the MyDataHelps app however, it is anticipated that subjects will become familiar with the app and explore its features given that their Fitbit data will be linked to the app and that their surveys will appear here as well.

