Research staff at UMMS will have a login name and password to access participant data, including adherence, physical activity, and survey data monitoring. Only study staff will have access to the participants' secure online database accounts. UMMS also has vulnerability scans that are conducted with the designated SCAP-approved vulnerability tool regularly. Devices are also adhered to the NIST Publication 800-123.

Mobile survey data and Fitbit data will be collected using a CareEvolution application called "MyDataHelps." Participants will sign an electronic consent form by entering their name and signature. Mobile survey responses will be de-identified since all data will be stored under a participant ID and will be transmitted to the secure CareEvolution server. Data transmitted to CareEvolution will be de-identified when extracted by the UMMS team. Information collected by the CareEvolution app will be securely stored on CareEvolution servers in the United States, or on servers owned by third party service providers that CareEvolution contracts with to securely store information in the United States. Data will be securely sent to UMass staff within one-week. The following link contains CareEvolution's security guidelines: <https://rkstudio-customer-assets.s3.amazonaws.com/CareEvolution/MyDataHelpsPrivacy.html>

The following security protocols will also be applied to all data: physical protections – all recordings and data will be stored on secure servers behind firewalls at UMMS. Additionally, UMMS has implemented a segregated environment for enhanced protection of systems that contain sensitive data. The data is housed and maintained outside of the regulated customer hosting environment which will in turn reduce the risk of cross contamination. The regulated environment is securely architected and supported by structured vetting and approval processes prior to access or system provisioning. All administrative access requires SSL VPN which utilizes multi-factor authentication.

INVESTIGATOR STUDY PLAN

All hard copy files will be locked in secure cabinets; logical protections – all recordings and data will be password protected and/or encrypted; and access protections – access will be granted to data on a need to know basis only.

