For Aim 3, we will recruit up to 15 participants, including: Cancer Clinic of the Ambulatory Care Center at the University of Massachusetts Memorial Hospital (UMMHC Clinic) patient navigators, advanced practice providers and oncologists/radiologists. Clinic staff will be recruited from our already existing relationships at the clinic. The Advanced Practice Provider charged with leading the Survivorship Task Committee will distribute an email describing the study to other Navigators in the Breast and Hemonc Clinics (see Survivor mHealth A3 Recruitment Email.docx). Providers will be recruited through existing clinical relationships, by also sending emails to providers and/or having our colleagues in the clinic distribute IRB-approved emails on the PIs behalf. Those interested in participating will contact the PI.

INVESTIGATOR STUDY PLAN

Compensation: All participants who take part in the study will receive a Fitbit to keep at the conclusion of the trial. Participants who complete the 12-week follow-up measures will receive a \$25 gift card within 2 weeks of completion. For those participants who wish to take part in the follow-up 30-minute interview and provider/clinic staff interviews, we will provide them with a \$25 gift card within 2 weeks of their completed interview.

25. Local Number of Subjects

We would like the IRB to approve the recruitment of up to 50 participants total. Within this 50, we request approval for 35 participants in Aim 1 to allow for attrition and loss to follow-up, in order to achieve our goal number of 25-30 study participants completing the study. The same participants will be included in Aim 2 interviews. We then request for approval for up to 15 participants in Aim 3 for provider/clinic staff interviews.

26. Confidentiality

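### MARS app usability is collected only through the app being rated, so each wave's summary leaves out people not using the app, and no set step asks non-users why

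*Combined protocol and SAP*

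**What the plan says.** **Route.** Section 11 (Aim 1 Procedures) states: "Through the MyDataHelps app, participants will complete a set of surveys". The waves fall at 24 hours, 1 month and 3 months. Section 13 (Data Security) repeats the route: "Mobile survey data and Fitbit data will be collected using a CareEvolution application called" MyDataHelps. The instruments are "Quality of Life Health Status (FACT-G), MARS (app usability), and Physical Activity", and Table 2 lists all three at every wave. No REDCap, telephone or paper version is described in the procedures. Section 16 mentions surveys on paper once, while discussing storage, with no procedure behind it.

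**Purpose.** Section 11 says that "the main purpose of these surveys is to make sure we can successfully obtain data and to receive feedback on the usability of the devices"; the same sentence also names the app. Section 10 makes feasibility primary and lists usability next: "Secondary Outcome Measure: To assess usability, physical activity, and quality of life health outcomes measures".

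**What surrounds the surveys.** MyDataHelps sends smartphone prompts for the surveys. Staff may telephone people who have technical or adherence difficulties. Table 2 tracks complete, incomplete, overdue and closed surveys by wave, and Table 3 tracks device syncing and wear. The Aim 2 interview (Section 11) takes place by telephone or Zoom, is optional, and is offered by email once a participant has finished the study tasks.

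**Numbers and analysis.** Section 25 gives the Aim 1 request as "35 participants in Aim 1 to allow for attrition and loss to follow-up, in order to achieve our goal number of 25-30 study participants"; the goal refers to those who finish the study. Section 13 plans aggregate descriptive statistics for the survey data, with no stated denominator and no rule for missing responses.

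**The concern.** The surveys serve two purposes: to show that data can be captured, and to learn how usable the system is. With a single route, the second answer exists only where the first is yes. Whether a person returns a MARS score at a given wave plausibly depends on how well the app works for that person, which is what MARS measures.

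At stake is the feedback this pilot is meant to gather before a larger trial. The people best placed to explain why the app is not used are the least likely to be heard through it. In-app prompts may not reach someone who has not installed the app. The telephone call is discretionary and meant for troubleshooting, not for recording a rating or a reason.

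Non-use is a realistic prospect. Section 30 provides a consent route for people without internet access, although Section 6 requires a smartphone, and Section 24 aims to oversample socioeconomically disadvantaged participants.

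**Working it through.** **Who has a MARS score under the plan as written**

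| Participant | 24 hours | 1 month | 3 months | Offered Aim 2 interview |
|---|---|---|---|---|
| Completes every wave | yes | yes | yes | yes, if all other tasks are done |
| Stops after the 1-month survey | yes | yes | no | not as written |
| Stops after the first survey | yes | no | no | not as written |
| Never gets the app working | no | no | no | not as written |

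The gap is total only in the last row. In the two middle rows it opens after the last completed wave. The first score is a limited substitute for later ones: it is due a day after enrolment, and devices may be posted after consent, so it may reflect little use.

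**Planned non-completion.** Inputs are from Section 25: 35 enrolled, 25 to 30 completing. (The total is consistent: 35 + 15 = 50.)

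- 35 − 30 = 5, and 5/35 = 14.3%
- 35 − 25 = 10, and 10/35 = 28.6%

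This is attrition for any reason. The plan does not say how much of it would be due to the app.

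**Effect on a responders-only mean.** With N enrolled, m missing, and a gap g (mean among responders minus the mean that the missing would have given):

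responders' mean − mean over all N = (m/N) × g

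The documents give no value for g, so the values below are assumptions. All 5 or 10 are taken as missing.

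| Assumed gap g (points) | m = 5 | m = 10 |
|---|---|---|
| −0.5 (missing would rate higher) | −0.07 | −0.14 |
| 0 | 0 | 0 |
| 0.5 | 0.07 | 0.14 |
| 1.0 | 0.14 | 0.29 |
| 1.5 | 0.21 | 0.43 |

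For example, (10/35) × 1.5 = 0.43.

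**Limit of this arithmetic.** It supposes that every missing person has a rating to give. Someone who never opened the app has no experience to score on a usability scale. For that person the useful information is the fact of non-use and the reason for it. The formula fits people who used the app and then did not rate it at that wave.

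**The case against.** The strongest reply is that non-use is already visible. Feasibility is the primary outcome, successful data capture is a stated purpose of the surveys, and Tables 2 and 3 report non-completion and non-syncing. A thin MARS response would sit beside those figures. Staff may telephone people who struggle with surveys, the dashboard is refreshed once or twice a day, and Section 25 says the same participants will be included in Aim 2. Usability is a secondary, descriptive outcome with no threshold attached.

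Much of this stands. It rules out several stronger readings that a reader might infer:

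- **That usability will be overstated.** The documents give no rating difference between responders and non-responders. With no difference the bias is zero, and it could reverse.
- **That people who leave the app never rate it.** Those who stop after the first or second wave have already given a score.
- **That 5 to 10 people are app failures.** Section 25 allows for all attrition and loss to follow-up.
- **That problems with the app would go unseen.** Their frequency is tracked, and some may surface in calls or interviews.
- **That FACT-G and the activity survey share the usability problem.** They do not measure usability. For them this is ordinary selective missingness.

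The reply does not supply the reasons. The tables give counts, the calls are optional and have no stated recording of reasons, and Section 11 offers the interview only after study tasks are done. The sentence in Section 25 does not change that timing.

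**Conclusion.** The point holds in a limited form. The procedures describe no route for MARS other than the app it rates, so each wave's summary is conditional on continued app use, and no planned step reliably collects reasons from those who drop out of it. Upward bias is the plausible direction but is not demonstrated.

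As an illustration, the shift is 0.07 to 0.43 points. That rests on two assumptions: a gap of 0.5 to 1.5 points, and all 5 to 10 planned non-completers being missing from MARS for that wave. If fewer are missing, the shift is proportionately smaller. No stated decision depends on the MARS mean, so the main loss is information for refining the programme. The change is still worth making because it is cheap and serves the pilot's own purpose.

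**What to change.** 1. Keep in-app completion exactly as it is for the feasibility count.
2. When a 1-month or 3-month survey shows as overdue or closed, or an enrolled participant never registers, send a short REDCap link or telephone. Ask the reason for non-use. Add MARS only for those who have used the app. Flag these responses by mode.
3. Offer the Aim 2 interview to non-completers as well as completers.
4. Report MARS for in-app responders and for all respondents, each with the number responding out of all enrolled.
5. Reconcile the mention of paper surveys in Section 16 with the app-only procedure in Section 11.

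The cost is one short REDCap form and a few extra contacts, for roughly 5 to 10 people on the plan's own figures. REDCap, staff calls and the dashboard are already in place. The downside is a possible mode effect, which the flag and the separate reporting keep visible.

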11. PROCEDURES INVOLVED

METHODS

Population: We will include a total of up to 35 cancer survivors and 15 providers/clinic staff.

Setting:

INVESTIGATOR STUDY PLAN

This study will mainly take place at the University of Massachusetts Medical School, with remote recruitment allowing for participants to partake in study activities outside of the institution. Analysis of the Fitbit and MyDataHelps survey app data will be taking place using secure medical school computers, in a secure office space. Additionally, data from the Fitbit and MyDataHelps survey app will be transferred from the Fitbit and MyDataHelps to CareEvolution and UMMS via secure SFTP (Secure File Transfer Protocol) servers that are compliant with HIPAA requirements. The SFTP server ensure that only intended authorized personnel can receive data and that transmissions are protected with strong encryption algorithms.

Aim 1 Procedures:

The research assistant (RA) will send eligible participants a secure inquiry email that will contain information about the study and ask if they would be interested in participating. If participants are interested in joining the study, they will be instructed to click a secure REDCap link in the inquiry email. This link will direct them to an electronic consent form. If the individual would like to participate in the study, they will provide their electronic signature. They will also have the option to do this over the phone/Zoom guided by research staff through the REDCap form or a consent form that was emailed to them. They will then be able to provide verbal consent with research staff if they are unable to access the REDCap online form.

All participants will receive a Fitbit to keep as part of their compensation for participating. The participant may also choose their preferred way of delivery of the device such as in-person or through the mail. Once the consent form is completed, the RA will give or send the participant their study devices. Participants will also receive instructions on how to set up their devices and link their Fitbit via a secure email after we give them their device(s). In these instructions we will inform the participant how to create and log into the smartphone applications and use the device(s). Participants will also be instructed to wear their Fitbit for a total of 3 months.

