from the CareEvolution platform). We will interview UMMHC medical providers, with a purposeful sample of at least one navigator from the Hematology/Oncology and one from the Breast clinic, as these are two of the largest clinics at the hospital.

Table 2. CareEvolution Survey Data Elements

Overview (cumulative enrollment data)	Domains
Participants	
Enrollment date	
Total # Participants Eligible	
Total # Participants Enrolled	
Total # Participants by Site	
Age	Baseline Enrollment Monitor
Gender	
Type of Phone:	
Android	
IOS	
Fitbit provided	
Surveys delivered at baseline (24 hours after enrollment)	
% complete	
% incomplete	Survey Wave 1
% overdue	
% closed	(Physical Activity, FACT-G, MARS (app usability))
Average days to complete survey	
Average time (sec) spent in surveys	
Steps (number of clicks)	
Surveys delivered at 1 month	
% complete	
% incomplete	Survey Wave 2
% overdue	
% closed	(Physical Activity, FACT-G, MARS (app usability))
Average days to complete survey	

INVESTIGATOR STUDY PLAN

Average time (sec) spent in surveys	
Steps (number of clicks)	
Surveys delivered at 3 months	
% complete	
% incomplete	
% overdue	
% closed	
Average days to complete survey	
Average time (sec) spent in surveys	
Steps (number of clicks)	
Surveys delivered overall	
% complete	
% incomplete	
% overdue	
% closed	
Average days to complete survey	
Average time (sec) spent in surveys	
Steps (number of clicks)	

Survey Wave 3

(Physical Activity, FACT-G, MARS
(app usability)); Qual interviews

Surveys Overall

Table 3. CareEvolution Fitbit Data Elements

Adherence Metrics	
	Any participant data
	Last device sync
	More than 14-days since last sync
	Total Days Worn (avg.)
	Wear Time (avg. minutes/day)
Summary of Variables	
All Heart Rate Data	Heart rate (daily average)
	Resting heart rate (daily average)
	Resting

INVESTIGATOR STUDY PLAN

	Minimum
	Maximum
All Step Data	Steps total (daily)
	Steps average (over 1 week)
	Steps average (over 1 month)
All Sleep Data	Sleep (avg. hours/night)
	Wake
	REM
	Light
	Deep
All Physical Activity Data	Physical Activity (avg. minutes/day)
	Light
	Moderate
	Intense
All Calorie Data	Calories (avg./day)
	Floors (avg./day)

12. Data and Specimen Banking*

N/A

13. Data Analysis and Management***Data Analysis**

Quantitative data (Aim 1) collected from surveys will be analyzed by calculating aggregate descriptive statistics (due to the small sample size) using STATA version 15.

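### Does Section 13 need to commit to paired change in the repeated Aim 1 surveys, so that selective dropout is not read as change?

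*Combined protocol and SAP*

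**What the plan says.** The quantitative analysis plan is a single sentence in Section 13 (Data Analysis): "Quantitative data (Aim 1) collected from surveys will be analyzed by calculating aggregate descriptive statistics (due to the small sample size"), carried out in Stata. It does not say whether each wave is summarised in all responders or in the same people, and it does not define a change score.

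The schedule is in Section 11 (Aim 1 Procedures): "participants will complete a set of surveys at 24 hours after their enrollment, 1 month, and 3 months after enrollment". FACT-G, MARS and Physical Activity are given each time. The same section states why the surveys are there: "the main purpose of these surveys is to make sure we can successfully obtain data and to receive feedback on the usability".

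Section 10 makes feasibility the primary outcome. The secondary outcome begins "To assess usability, physical activity, and quality of life health outcomes measures", with no time point or contrast named.

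Section 25 requests 35 Aim 1 participants "to allow for attrition and loss to follow-up, in order to achieve our goal number of 25-30 study participants completing the study".

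Section 13 (Data Security) makes pairing possible: "Mobile survey responses will be de-identified since all data will be stored under a participant ID". Table 2 lists the number enrolled and the completion status of the surveys at every wave.

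On the Fitbit, Section 32 says "The study will deploy a Fitbit device to all participants to track progress of their physical activity", and Section 11 (Setting) says "Analysis of the Fitbit and MyDataHelps survey app data will be taking place using secure medical school computers". Section 10 does not say whether the physical activity outcome comes from the survey, the device or both.

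**The concern.** Three waves of the same instrument, the first labelled as baseline in Table 2, invite comparison across the row. If the Wave 1 column averages everyone who answered and the Wave 3 column averages those who stayed, the difference mixes real change with a change in who is averaged. Suppose people with poorer quality of life or lower activity leave more often. FACT-G and activity would then appear to improve although nobody improved. The programme is meant to raise physical activity and the pilot is meant to inform a larger trial, so a false impression of improvement could carry forward.

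Pairing looks cheap. Responses are stored by participant, no new data are needed, and a within-person mean avoids averaging different people at the two waves. Table 2 shows how many complete each wave, but not whether those lost differed at the start.

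**Working it through.** The documents give no power, precision or dropout calculation to reproduce. The only planned figures are 35 enrolled and 25 to 30 completing (Section 25).

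**Implied loss.** (35 - 30)/35 = 14.3%; (35 - 25)/35 = 28.6%. This treats the ceiling of 35 as actual enrolment and supposes that everyone lost answered Wave 1.

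**Shift in unpaired wave means when nobody changes.** Shift = loss × gap, where gap is the stable difference between completers and dropouts in SD. The gap is not in the documents; the range below is assumed.

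| Completers | gap 0 | gap 0.25 | gap 0.5 | gap 0.8 |
|---|---|---|---|---|
| 30 (loss 0.143) | 0 | 0.036 | 0.071 | 0.114 |
| 25 (loss 0.286) | 0 | 0.071 | 0.143 | 0.229 |

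A simulation (20,000 runs per setting, 35 enrolled, no true change, dropout driven by a person's stable level, two strengths of selection) gave unpaired shifts of 0.151 and 0.238 SD with 25 completers, and 0.077 and 0.127 SD with 30. The paired change stayed within 0.003 SD of zero. When change itself was linked to the stable level, the paired mean was off by 0.02 to 0.07 SD, against 0.10 to 0.31 SD unpaired.

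**Precision of a paired change.** Half-width = t × √(2(1 - r)/n), with r the correlation between waves (assumed 0.5, so the SD of change equals the SD at one wave).
- n = 25: SE = 1/√25 = 0.200; 95% half-width 0.413 SD.
- n = 30: SE = 1/√30 = 0.183; 95% half-width 0.373 SD.
- For r from 0.3 to 0.7: 0.488 to 0.320 SD (n = 25) and 0.442 to 0.289 SD (n = 30).

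**When dropout follows the observed Wave 1 score.** Take 25 completers, a gap of 0.5 SD in the Wave 1 score itself, and r = 0.5. Completers start 0.286 × 0.5 = 0.143 SD above the mean of all 35. With no true change they regress to 0.5 × 0.143 = 0.071 SD above it at Wave 3. The unpaired difference is therefore +0.071 SD, and the paired change is 0.071 - 0.143 = -0.071 SD. Pairing reverses the sign and leaves the size the same.

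**Comparing completers with non-completers at Wave 1.** The 95% half-width of the difference is t × √(1/n₁ + 1/n₂), with t = 2.03.
- 25 v 10: 2.03 × √(0.040 + 0.100) = 0.76 SD.
- 30 v 5: 2.03 × √(0.033 + 0.200) = 0.98 SD.

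Both exceed the assumed 0.5 SD gap, so such a table could not tell that gap from none.

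**The case for a change.** The strongest argument for a change is that it is nearly free. A mean paired change with its SD is descriptive and aggregate, so it fits the plan's reporting rules and needs no test or larger sample. Fixing the summary beforehand also stops anyone choosing it after seeing the data. Table 2 counts completions but does not connect them to the outcome summaries.

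The factual part stands: Section 13 does not specify the summary, no other section does so, and unpaired wave means can mislead when dropout is selective. The argument that pairing must be written in is weaker. If paired change is already an aggregate descriptive statistic, the present sentence allows it. The harm needs a before-after reading that no aim, endpoint or hypothesis calls for.

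The proposal also has costs. Change from Wave 1 for three instruments at two later waves makes six single-arm estimates with intervals, which could encourage the very reading it is meant to prevent. MARS is a poor candidate: Wave 1 falls 24 hours after enrolment, and Section 11 has devices handed over or mailed only after consent, so early answers may reflect little or no use. People who never answer Wave 1 stay invisible to pairing.

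The unstated source of the physical activity outcome, and any wear-time threshold for the Fitbit, are separate questions of specification. They add no weight here, and no size is claimed for them.

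**Conclusion.** No change is needed. This is missing detail that analysts can fill sensibly: they can put the number responding beside each wave's mean and, where useful, give within-person change for FACT-G and Physical Activity, described as applying to completers only. The existing wording and the stored data already permit both.

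The possible distortion is modest: 0.04 to 0.23 SD for assumed gaps of 0.25 to 0.8 SD, and nil if dropout is unrelated to outcome. Even the largest value lies inside the 0.37 to 0.41 SD half-width that a paired estimate would carry at r = 0.5. The gap and r are assumptions, not figures from the documents. The 14% to 29% loss supposes that enrolment reaches 35, although Section 24 reports that the recruitment routes tried earlier had brought in nobody.

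Pairing removes the distortion only if dropouts differ stably from completers; it does not remove regression to the mean. With feasibility as the primary outcome and the surveys meant chiefly to test data capture and gather usability feedback, the plan followed as written gives sound results for what it sets out to learn. The conclusion would differ if a before-after claim were added to the endpoints.
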